Study Procedure	
 1) Pre-screening by clinical staff per SOP220 to identify potential subjects who would likely meet the criteria for participation in the study. 2) Recruitment Flier is provided electronically and/or hard copy is mailed out with trial Obi Gen3 Medical Robot with triadic recruitment strategy (Provider, Caregiver, Patient) 3) Screening: In-office assessment performed by provider to determine eligibility for home/community trial per Standard Operating Procedures (SOP220) that would be completed regardless of whether participating in the study. While this is not specific to the study procedure, it has been included here to help clarify the process. 4) Informed consent will be obtained for all stakeholders interested in participating (Provider, Caregiver, Patient) electronically using Qualtrics 5) ~ One (1) week home/community trial of Obi Gen 3 with a minimum of a five (5) meal requirement for use by Caregivers and

	
Patients. Providers must recommend and assess at least one (1) patient for Obi Gen 3 in their practice setting.
 
6) Following the ~ one (1) week trial, Qualtrics will send an electronic web-based link.
 
7) Participants who complete the surveys will receive a \$25 electronic gift card
 
8) Optional: Follow-up interviews completed by telephone, if warranted, within one (1) month of survey completion.

Schedule of Events	
1) Pre-Screening
 
2) Recruitment, electronic and paper flyers
 
3) Screening (In-office assessment)
 
4) Informed Consent
 
5) ~One Week Obi Gen3 trial
 
6) Survey completion
 
7) Provide \$25 remuneration
 
8) Optional follow-up interviews

A.2. Identification and description of the Investigational Device

[figure not shown]
[figure not shown]
a) Summary Description of Investigational Device

Obi is a reusable robotic utensil intended to compensate for the function of a human arm during mealtime activities to restore a person's functional eating (self-feeding) status. Obi alleviates/ameliorates the disability caused by medical diseases/conditions that completely or severely impair the upper extremities/limbs. Obi provides a cross-cultural, broad user demographic with the ability to make decisions on what and when to eat through an easy-to-learn and use user interface.

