feeding for individuals with upper extremity impairments—a key activity of daily living that contributes to personal dignity, autonomy, and quality of life.

The claims for clinical performance and effectiveness to be verified in this study include:

- The device can be safely and effectively operated by the intended users (patients and caregivers) in a home, school, or community setting.
- The device is recommended and integrated into practice by clinical professionals who support individuals with feeding-related disabilities.
- The design features, controls, and user interface support efficient, effective, and satisfactory use.
- The device enables users to independently complete a minimum of five meals during a one-week trial period without undue burden on caregivers or providers.

This clinical investigation also aims to verify that supporting materials (e.g., Quick Start Guide, Instructions for Use, and MDNA form) are usable and that the overall user experience aligns with expectations for performance, ease of use, and satisfaction. These claims will be evaluated through mixed-methods data collection, including surveys and semi-structured interviews. No safety claims are being assessed in this study. Obi Gen 3 is a Class I medical device with minimal risk and has undergone benefit-risk analysis and mitigation per ISO 14971. However, participants will be monitored for device-related issues or unanticipated problems during the trial.

b) Objectives, primary and secondary, are described as ‘superiority,’ ‘non-inferiority,’ or ‘equivalence,’ if applicable.

PRIMARY: Validate whether the production equivalent enhanced Obi3 device design conforms to the formally defined user needs and intended use (per IFD-DES-054-1, Obi Validation Plan, Gen3)

SECONDARY:

- Determine patient usability in accordance with the Matching Person & Technology Assistive Technology Framework.
- Determine caregiver usability in accordance with questions from the Caregiver Burden Index.
- Determine provider perspectives following the SUS as a standardized outcome measure.
- Obtain provider feedback regarding the efficacy, efficiency, and satisfaction of the Obi clinical assessment forms and the associated process.
- Obtain other qualitative feedback regarding the perceived strengths and weaknesses of the Obi design.

c) Scientific justification and clinical relevance for effect sizes, non-inferiority margins, or equivalence limits, where applicable.

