3. **Provider perspectives and Workflow Integration** will be measured using the System Usability Scale (SUS) and open-ended feedback. The study will assess ease of device recommendation, assessment form clarity, and integration into the service delivery process.
4. **Effectiveness of Training and Support Materials** will be assessed via post-trial feedback on the Quick Start Guide, Instructions for Use, and clinical assessment documentation (Obi MDNA©).

Rationale: These endpoints reflect stakeholder-specific criteria for acceptability, feasibility, and usability and were selected based on established frameworks in the assistive technology literature.

d) Methods and timing for assessing, recording, and analyzing variables.

This clinical investigation employs a mixed-methods approach to assess the usability and user experience of the Obi Gen 3 Medical Robotic Feeding Device. Both quantitative and qualitative variables will be assessed at multiple timepoints using standardized and non-standardized tools. Data will be recorded electronically and analyzed using descriptive and thematic methods.

Key variables to be assessed include:

- **Usability metrics** (efficiency, effectiveness, satisfaction)
- **Stakeholder-specific experience and acceptance** (patients, caregivers, providers)
- **Functional outcomes** related to self-feeding independence
- **Psychosocial impact** (confidence, autonomy, perceived burden)
- **Feedback on supporting materials** (ease of use of training guides, forms)

As previously described, these variables will be measured using quantitative surveys and rating scales, including the System Usability Scale (SUS) and Matching Person & Technology (MPT) Framework.

Qualitative data will be gathered through open-ended questions, which are included in the surveys, and semi-structured interviews conducted by phone, when applicable.

Timing of Assessments

- **Baseline:** Screening and in-office assessment by providers; completion of the Obi MDNA© form to gather demographics and baseline functional feeding status.
- **During trial:** One-week trial of Obi-Gen 3 in home, community, or school settings. Caregivers and patients use the device with at least five meals; providers recommend or assess at least one user in their practice.

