- Documentation of any protocol deviations, adverse events, or device-related issues;
- Completion of final data monitoring activities and closure of the Qualtrics data collection system;
- Submission of a final study report following applicable IRB and sponsor requirements.

A.6.2. Investigational Devices and comparators

a) Description of the exposure to the investigational device(s) or comparator(s), if used.

This clinical investigation involves exposure to a single investigational device, the Obi Gen 3 Medical Robotic Feeding Device, which is a production equivalent version of a Class I FDA-registered medical device intended to assist individuals with upper extremity impairments in self-feeding. Participants in the study—including patients, caregivers, and providers—will be exposed to the device during a short-term, observational usability trial, which occurs under real-world use conditions (home, school, community, or clinical environments). No comparator device is being used.

All exposure to the device is consistent with its intended purpose and involves no modification to existing standards of care or risk to participants. The exposure is limited in duration and is conducted in naturalistic settings to allow the device to be evaluated under realistic use conditions.

Patient and Caregiver Exposure: Patients and caregivers will use the Obi Gen 3 device for a period of approximately one week. During the trial, users are expected to operate the device for a minimum of five meals, though additional use is encouraged to gather meaningful feedback. Participants will use the device independently or with caregiver assistance, following a brief orientation via a Quick Start Guide (QSG) and Instructions for Use (IFU) provided with the device. Device use is non-invasive and involves no physical contact beyond standard utensil-based feeding.

Provider Exposure: Providers (e.g. occupational therapists, speech-language pathologists, assistive technology professionals) will interact with the Obi Gen 3 device in the context of:

- Assessing its fit for at least one patient in their caseload,
- Recommending its use as part of routine practice (if applicable),
- and Providing feedback based on observation or guided use in their clinical setting.

The Providers will not operate the device for feeding themselves but will assess functionality, usability, and alignment with therapeutic goals.

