- **Providers** - Licensed healthcare professionals with direct experience in recommending, assessing, or implementing assistive technology, rehabilitation interventions, or feeding-related supports. This may include, but is not limited to, occupational therapists (OTs), speech-language pathologists (SLPs), assistive technology professionals (ATPs), and other qualified providers actively engaged in supporting individuals with self-feeding challenges.
- **Caregivers** - Individuals who provide regular, hands-on support to a person who may benefit from using the Obi Gen 3 device. This includes family members, personal care aides, educational support staff, or other support personnel who assist with or supervise feeding activities in the home, school, or community setting.
- **Patients:** Adults or children aged 5 years or older who require assistive technology to support independent or supported self-feeding due to upper extremity motor impairments or related

functional limitations. Individuals must have the cognitive and physical ability to participate in the one-week usability trial, either independently or with the assistance of a caregiver.

All participants must be able to understand and comply with study instructions and provide consent or assent (when applicable) either by themselves or through a legally authorized representative.

b) Exclusion Criteria for Subject Selection

Participants will be excluded from the study if they meet any of the following conditions:

- Individuals who cannot provide informed consent or assent, either due to legal status, cognitive limitations, or other conditions that impair decisional capacity.
- Individuals with severe cognitive impairments that would preclude meaningful participation in the study's usability tasks, including the ability to interact with the device or provide relevant feedback.
- Non-English-speaking individuals, as all study materials—including consent documents, surveys, and instructions—are available only in English at this time, and interpreter services are not being utilized in this investigation.
- California residents who are new to using Obi. The state of California requires a one-month trial, so the one-week timeline will not be feasible for California residents.

c) Criteria and procedures for subject withdrawal or lost to follow-up

i) when and how to withdraw a subject from the clinical investigation or stop the use of the investigational device,

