Each subject's participation in the clinical investigation will vary based on their role (provider, caregiver, or patient) and level of engagement. The core duration of participation for all enrolled stakeholders is approximately one week, corresponding to the required trial period of the Obi Gen 3 Medical Robotic Feeding Device in a home, school, or community setting.

- **Patients and Caregivers:** Participants are expected to use the device for at least five meals over a one-week period. During this time, they will use the device in real-life contexts and later complete post-trial surveys and optional follow-up interviews.
- **Providers:** Participating providers are expected to conduct an initial in-office assessment to determine patient suitability for the Obi Gen 3, recommend at least one patient for trial use, and provide feedback based on their clinical observation. Their involvement also includes completing a usability survey post-trial and, if applicable, participating in a brief follow-up interview.

Follow-up through telephone-based semi-structured interviews may be conducted within one month to further clarify or expand responses to open-ended questions. These interviews will be scheduled within one month of the trial's completion.

h) Number of subjects required to be included in the clinical investigation, and where needed, anticipated distribution of enrolment among the participating investigation sites.

A total of 60 participants will be recruited using flyers and word-of-mouth strategies

Stakeholder Group	Target Sample Size
Providers [Occupational Therapists (OTs), Assistive Technology Professionals (ATPs), Speech Language Pathologists (SLPs), and other relevant providers)	20 in various practice settings
Caregivers (family members, aides, support personnel)	20 (5 for adults, 15 for children)
Patients (adults and children using Obi Gen 3)	20 (5 adults, 15 children)

i) Estimated time needed to select this number (i.e. enrolment period).

The estimated time required to enroll the whole sample for this usability study is 4–5 weeks, given the study's targeted outreach strategy, electronic recruitment methods, and existing professional and caregiver networks available to DESIN LLC and the investigative team. Recruitment materials, including flyers and direct outreach, will be distributed electronically and through participating service providers to expedite enrollment.

j) Relationship of investigation population to target population.

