Given the short duration and minimal risk nature of this usability study, the expected drop-out rate is anticipated to be low (less than 10%). Participants will be engaged for a one-week home or community-based trial of the Obi Gen 3 device,. The limited time commitment, non-invasive nature of participation, and flexibility of remote data collection (via Qualtrics and telephone interviews) are expected to support high retention.

Potential reasons for early withdrawal or loss to follow-up may include:

- Lack of interest or time to complete the trial period or follow-up activities
- Health-related issues or changes in caregiving responsibilities
- Technological issues or accessibility barriers (e.g., inability to access electronic surveys)
- In rare cases, discomfort or dissatisfaction with the device

Because the study does not involve treatment, diagnostic procedures, or invasive interventions, death is not anticipated and is not an endpoint. Any withdrawal or loss to follow-up will be documented with reason, when available. Data collected prior to withdrawal will be included in the analysis, consistent with an as-treated approach.

f) The rationale for the number of procedures to be performed by a single user as part of the learning curve and how these data are to be analysed, if applicable.

Given that this investigation evaluates the usability of a robotic feeding device designed for individuals with upper extremity impairments, caregivers, and providers, it is important to account for the initial learning period associated with device setup, operation, and integration into daily routines. The one-week trial period with a minimum expectation of five completed meals per patient/caregiver dyad is designed to reflect a realistic and sufficient exposure to allow users to become familiar with the device and overcome early learning curve effects.

This threshold was selected based on preliminary feedback from internal evaluations and stakeholder consultations, which indicated that users typically require **3–5 sessions**, to feel comfortable with basic functions (e.g., powering on, positioning the spoon, switching food compartments). For providers, the requirement to recommend and assess at least one patient supports evaluation of the device within their existing workflow, allowing observation of setup, training, and follow-up in a practical setting.

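### Three sections make recommending a patient for an Obi3 trial part of the provider role, so participation cannot verify the claim that clinicians recommend the device, and two other sections contradict the requirement

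*Protocol*

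**What the plan says.** A.5 a) lists four claims that the study is to verify. One of them is "The device is recommended and integrated into practice by clinical professionals who support individuals with feeding-related disabilities".

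Three sections make recommending part of the provider's role:

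- A.1.5, Study Procedure, step 5: "Providers must recommend and assess at least one (1) patient for Obi Gen 3 in their practice setting".
- A.6.3 g): providers are expected to "recommend at least one patient for trial use, and provide feedback based on their clinical observation".
- A.7 f) calls it a requirement: "the requirement to recommend and assess at least one patient supports evaluation of the device within their existing workflow".

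Two sections are looser. A.6.1 d) has "providers recommend or assess at least one user in their practice", and A.6.2 a) makes recommendation conditional ("Recommending its use as part of routine practice (if applicable").

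The provider inclusion criterion in A.6.3 a) asks for "Licensed healthcare professionals with direct experience in recommending, assessing, or implementing assistive technology, rehabilitation interventions, or feeding-related supports". Neither it nor the synopsis criterion asks for a recommendation of Obi3.

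**The concern.** A claim is verified only if the study could have shown it to be false. Where recommending a patient is a condition of fulfilling the provider role, the finding that providers recommended the device follows from the rule and carries no information about Obi3.

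The second issue is who answers the provider survey. A provider who assesses a patient and does not send that patient to a trial fails the requirement as three sections word it, and has no clear route to the survey. A.5 d) places the value of the study in finding facilitators and barriers to use, and such a provider is an obvious source on barriers. The provider result also matters for the decision: A.7 g) requires the thresholds to be met in all stakeholder groups, so the provider group is one of three that must pass. Neither the selection-bias text in A.7 i) nor the list of foreseeable factors in A.6.4 c) mentions this filter.

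**Working it through.** **1. The claim against the role.** The provider target is 20 (A.6.3 h). If A.1.5, A.6.3 g) and A.7 f) are followed, the share of participating providers who recommended at least one patient is 20/20 = 100% by construction. No section defines a denominator of providers who assessed, and A.7 g) sets no threshold for recommendation. The other half of the claim, integration into practice, is not fixed by this rule.

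**2. The route of a provider whose only assessed patient is unsuitable.**

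| Step | Section | Consequence |
|---|---|---|
| Office assessment comes before consent | A.1.5, Study Procedure, steps 3 and 4 | The provider has judged the patient before agreeing to take part |
| Enrolment needs both consent and a completed office assessment | A.6.3 d) | Same order |
| Only favourable office assessments go on to the home trial | A.4 e) | No trial for this patient |
| The survey link follows the trial | A.1.5, step 6 | Nothing triggers a survey for this provider |
| The 50% user-needs rule counts those who complete the one-week trial | A.7 g) | No clear place in the denominator |

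A.7 a) would analyse anyone who consents and completes a survey, but no step sends this provider one. The filter therefore does not rest on the wording of the requirement alone.

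**3. Direction and possible size.** The documents give no refusal rate and no rate of favour by recommendation, so there is no plan figure to reproduce. The following is illustration only, with assumed rates. Let s be the share of assessing providers who recommend, a the favour rate among those who recommend, and b the rate among those who do not. Then p = s·a + (1 − s)·b. With 20 respondents the 50% rule needs at least 10 in favour, so the chance of passing is P(X ≥ 10) with X binomial(20, p). Example: s = 0.5, a = 0.70, b = 0.10 gives p = 0.35 + 0.05 = 0.40 and a chance of 0.245.

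| a / b (assumed) | Recommenders only | All assessing, s = 30% | s = 50% | s = 70% | s = 90% |
|---|---|---|---|---|---|
| 60% / 10% | 0.872 | 0.014 | 0.122 | 0.409 | 0.751 |
| 70% / 10% | 0.983 | 0.030 | 0.245 | 0.657 | 0.935 |
| 80% / 20% | 0.999 | 0.190 | 0.588 | 0.908 | 0.995 |

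If a = b, p no longer depends on s and the filter has no effect. If non-recommenders are less favourable, the filter moves the result towards passing.

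In counts, again assumed: 28 providers assess, 20 recommend, and 11 of those 20 are in favour, so 11/20 = 55%. If k of the other 8 are in favour, the rate among all assessing providers is (11 + k)/28: 39.3% for k = 0, 46.4% for k = 2, 50.0% for k = 3 and 67.9% for k = 8. The verdict changes only if at most 2 of the 8 are in favour.

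**The case against.** The strongest reply is that recommending here is not endorsing. A.6.3 g) speaks of trial use. It is a decision about one patient's suitability, taken before the trial, the follow-up assessment and the survey. A provider can send a patient to a trial and then score the SUS low or report unmet needs, and because one patient is enough, can decline others and still take part. This stands. A reader might infer that all provider ratings come from clinicians who favour Obi3; the documents do not support that. They support only that the ratings lean towards providers who found at least one suitable patient.

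A reader might also infer that a provider must recommend Obi3 to enter the study. The inclusion criteria do not say so, A.6.1 d) and A.6.2 a) would admit a provider who only assesses, and no section says such a provider is withdrawn. This also stands. It makes the matter a contradiction to be reconciled and does not show that the stricter wording governs, although the sequence in step 2 of the working filters in the same direction under either wording.

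Thirdly, A.5 a) says the claims are evaluated through surveys and interviews, A.6.1 c) looks at ease of recommendation, and no pass criterion turns on the share recommending. That is correct, and it limits the consequence: 100% would be a statistic the protocol never defines. It does not supply another test of the recommended half of the claim.

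Finally, a provider whose patient had no trial has had different exposure, and the primary endpoint is assessed after the trial week. Pooling the two kinds of provider in the A.7 g) result would mix exposures. This stands and shapes the fix.

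**Conclusion.** The point holds in a limited form. Under A.1.5, A.6.3 g) and A.7 f), participation itself satisfies the recommended half of one of the four claims in A.5 a), so participation cannot be used as evidence for it. A.6.1 d) and A.6.2 a) contradict those sections. Together with the sequence in A.1.5, A.4 e), A.6.3 d) and A.7 g), the rule tilts the provider survey and SUS towards providers who judged at least one patient suitable.

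The direction is towards passing if providers who do not recommend are less favourable than those who do, which is plausible but not shown. The size cannot be known from the documents: under the assumed rates the effect runs from negligible to decisive, and every figure in the illustrations beyond the 20 providers and the 50% rule is an assumption. It would go too far to say that the whole claim is circular, since integration into practice is not, or that the provider pass criterion is met by definition, since trial-recommending providers can answer unfavourably. Severity is moderate: it should be corrected before enrolment, and it does not by itself invalidate the design.

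**What to change.** 1. Reconcile A.1.5 step 5, A.6.3 g) and A.7 f) with A.6.1 d) and A.6.2 a), so that the provider role reads the same throughout: assess at least one patient with Obi3, whether or not a trial is then recommended.
2. Invite providers before the in-office assessment (A.1.5 steps 3 and 4, A.6.3 d, A.6.4 a). Send the provider survey and SUS to every consenting provider who assessed a patient, with a trigger that does not depend on a home trial.
3. Keep the user-needs result in A.7 g) on providers whose patient completed the trial. Beside it, report the responses of providers whose patient did not go on to a trial, and the result for all assessing providers. State in A.7 a) and A.7 g) where each group counts.
4. Evaluate the recommended part of the A.5 a) claim as providers recommending over providers assessing, and patients recommended over patients assessed, with reasons for not recommending. Otherwise remove it from the claims to be verified.

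The benefit-risk condition for the home trial in A.4 e) is not touched.

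The cost is wording in the sections named, an earlier provider invitation and one or two extra survey items, with no extra visits. The downside is that a few surveys will rest on the office assessment alone, and the result for all assessing providers may be slightly less favourable. Responses not collected at the time cannot readily be recovered later, so the change belongs before enrolment.
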